**Primary hypothesis testing:** 100 participants will be randomized in a 1:1 allocation to treatment with pramipexole or placebo. The primary assessment of safety will be based on the incident of adverse event rates and standardized mood ratings at each visit. Differences in the incidence of individual adverse events will be compared between randomization arms using Poisson regression. Exact 95% confidence intervals (based on the Poisson distribution) for the risk ratios for individual adverse events for treatment with pramipexole versus placebo will be computed and may incorporate an estimated overdispersion parameter if observed variability exceeds that determined by the Poisson distribution. Performance on the IGT will also be used to track potential changes in impulse-control (baseline, weeks 6 and 12). We will test for correlations between IGT performance and mania symptoms at the times of testing (simultaneous measurements). Moreover, we will use IGT change scores as predictors in regression models to evaluate changes in mania ratings at concurrent time points as well as future time points. This will directly address the question of whether or not changes in IGT strategy serve as markers of current mania and/or impending affective destabilization.

The relative specificity of pramipexole in binding to D2/D3 receptors allows for a unique opportunity to enhance DA in neural networks associated with specific aspects of cognition as well a reward processing, which will be carefully assayed in this study so that exploratory analyses will be able to test questions related to the role for these receptors across several interacting domains in BD, at least at the level of behavior. Exploratory analyses will include specific domains and individual tasks which will be modeled to account for main effects and interactions (as described in primary analyses below).

The primary outcome for efficacy is change in cognition from baseline to week 6 (MCCB Composite). The null hypothesis is that there is no difference in this change between

|   |   |  |
|---|---|--|
|  | Protocol Title:                           | 1/2-Pramipexole in Bipolar Disorder: Targeting Cognition (PRAM-BD) |
|   | Principal Investigator Name/Contact Info: | [name]   |
|   | Primary Contact Name/Contact Info:        | [name]
[contact]                          |
|   | Date Revised:                             | March 23, 2016 – date of IRB approval May 6, 2017                  |

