*Missing data:* Although the mixed effects modeling approach allows patients with evaluations at week 4 but missing at week 8 to be included, bias may be introduced if missing data are related to patient response. For example, it may be that patients responding poorly are less likely to have a week 8 evaluation than those patients with better response. The mixed effects analysis would weigh the results of these poorly performing patients less (as they provide fewer data) and in the presence of a positive effect of pramipexole, decrease power. To assess the extent that any bias has been introduced by missing data, we will impute missing week 8 values. Note that if no bias is produced by the missing data, analyses with and without imputation should provide virtually identical results. If the analyses produce different results, we will work to identify the causes by comparing patients with and without missing data. Based on our prior trial experience we expect relatively few patients (< 10) to be missing the week-8 visit due to attrition. Patients with missing data will have their 8 week MCCB score imputed via multiple imputation assuming that the data are MAR, i.e., the missing nature of the variable is independent of the value of the variable given the observed data. The specific imputation model to be used will be determined prior to examination of any outcome data, but will include MCCB score at baseline and at 4 weeks. Separate imputations will be done for each randomization group.

*Due to the 12 week course of the study, mixed models will still be utilized for variables collected with sufficient frequency; however, when incorporating missing data, we will only be able to do so when at least two time points are included. Subjects with only baseline data will be included in descriptive analyses but will be dropped for analyses where necessary.*

|   |   |  |
|---|---|--|
|  | Protocol Title:                           | 1/2-Pramipexole in Bipolar Disorder: Targeting Cognition (PRAM-BD) |
|   | Principal Investigator Name/Contact Info: | [name]   |
|   | Primary Contact Name/Contact Info         | [name]
[contact]                          |
|   | Date Revised:                             | March 23, 2016 – date of IRB approval May 6, 2017                  |
|   | Study Number:                             | GCO 13-0237, HS 14-00328   |

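### The missing-data check compares two analyses that both assume MAR, so it can hardly detect loss tied to unseen cognition, and no MNAR sensitivity analysis of the week-6 endpoint is planned

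*Combined protocol and SAP*

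**What the plan says.** Section 5h, Primary hypothesis testing, makes the primary efficacy outcome the change in MCCB Composite from baseline to week 6. It is tested by intention to treat in a mixed effects model with change as the dependent variable. The listed terms are a random patient effect, randomization group and the stratification indicators. No visit term is listed, and the section counts the use of both post-baseline evaluations as a gain in power.

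The Missing data paragraph says the mixed model "allows patients with evaluations at week 4 but missing at week 8 to be included". It warns that missingness may be related to response, and continues: "To assess the extent that any bias has been introduced by missing data, we will impute missing week 8 values". The method is "multiple imputation assuming that the data are MAR", run separately by arm, with a model that "will include MCCB score at baseline and at 4 weeks". If the analyses with and without imputation differ, patients with and without missing data will be compared. Expected loss is "relatively few patients (< 10) to be missing the week-8 visit due to attrition".

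A further paragraph adds that "when incorporating missing data, we will only be able to do so when at least two time points are included", and that "Subjects with only baseline data will be included in descriptive analyses but will be dropped for analyses where necessary".

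Sections 5e and 5f place MCCB at baseline, week 6 and week 12. Weeks 4 and 8 are study visits, but no MCCB is given at either.

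**The concern.** The plan names the right threat, patients leaving because they respond poorly, but its check shares the assumption that this threat would break. If loss depends on the MCCB score that was never seen, the mixed model and the MAR imputation are biased together and still agree. The check also imputes the later score, while the primary endpoint is the earlier one. Week 6 is exposed mainly through patients with no post-baseline MCCB, and these seem to be outside the comparison.

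The plan mentions only a loss of power. If poor responders are lost mainly from the pramipexole arm, the bias favours the drug. The documents make loss related to arm plausible. Titration runs to week 6 with discontinuation for intolerance (5f), mood exacerbation leads to discontinuation (5j), and the listed side effects include confusion and memory problems (section 6). As planned, the trial could not show how far its week-6 result depends on MAR or on leaving out patients without a week-6 score.

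**Working it through.** **The plan's own figure.** With 50 per arm, d = 0.55 and two-sided 0.05: 0.55/√(2/50) = 2.75, and Φ(2.75 − 1.96) = 0.785. This agrees with the stated power of approximately 80%, so 50 per arm is used below.

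**Step 1: the visits.** The Missing data paragraph imputes a week-8 score from baseline and week 4. MCCB exists only at baseline, week 6 and week 12. The natural reading is 6 for 4 and 12 for 8, but that is an inference and the passages must be reconciled. On that reading only the week-12 score is imputed, and imputation of a missing week-6 score is not described.

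**Step 2: how far the check can move.** Simulation assumptions (not in the documents): MCCB correlations 0.8, no true effect, 50 per arm, 20 imputations within arm. Nine patients lose the later score, and loss is related to the unseen change. Splits are pramipexole:placebo. The gap is the absolute difference between the two analyses, in SD of change.

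| Model, split 8:1 | Bias, mixed / imputed | Mean gap, informative loss | Mean gap, random loss |
|---|---|---|---|
| Arm-by-visit terms, week 12 | 0.099 / 0.098 | 0.017 | 0.016 |
| Arm-by-visit terms, week 6 | about 0 | 0.000 | – |
| Visits pooled, as 5h literally reads | 0.044 / 0.051 | 0.013 | 0.011 |

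A second run of the pooled model gave gaps of 0.014 and 0.012. The chance that the gap is larger under informative than under random loss was 0.52 (week 12) and 0.54 (pooled), where 0.50 means no discrimination. Imputing week 6 under MAR for baseline-only patients does not help: at 8:1 the biases were 0.134 and 0.122, and the gap was 0.022 against 0.020 under random loss.

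**Step 3: week-6 bias from baseline-only patients.** Suppose lost patients average 0.96 SD of change below retained patients (an assumption). An arm that loses L of 50 then has its mean overstated by 0.96 × L/50, so

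bias = 0.96 × (L_pramipexole − L_placebo)/50, SE = √(1/(50 − L_pramipexole) + 1/(50 − L_placebo)).

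With r = bias/SE, type I error = Φ(r − 1.96) + Φ(−r − 1.96).

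| Split of 9 | Bias | SE | r | Type I error |
|---|---|---|---|---|
| 5:4 | 0.019 | 0.210 | 0.09 | 5.1% |
| 6:3 | 0.058 | 0.210 | 0.27 | 5.9% |
| 8:1 | 0.134 | 0.210 | 0.64 | 9.8% |

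Nine is an upper case, because the plan's figure of fewer than 10 is for the later visit.

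**Step 4: how likely a lopsided split is.** With nine losses, P(at least 8 on pramipexole) = 10/512 = 0.020 if each loss is equally likely in either arm, and (9 × 2⁸ + 2⁹)/3⁹ = 0.143 if two-thirds of losses are expected there.

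**Step 5: against the design effect.** 0.134/0.55 = 24% if 0.55 is in SDs of change. If it is in score SDs, a correlation of 0.8 gives an SD of change of √(2 × 0.2) = 0.632, and 0.134 × 0.632/0.55 = 15%. The Sample size/Power paragraph does not say which.

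**The case against.** **The check has value.** At 8:1, in simulation, the chance of a larger gap than under random loss was 0.76 when loss was driven by baseline, and 0.92 when it was driven by a recorded variable in the imputation model. The plan fixes that model before outcome data are examined and does not exclude mood or side-effect variables. This stands, and is why the check should be kept.

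**The plan does not say that agreement proves absence of bias.** It says only that no bias implies near-identical results. That is fair, but the stated purpose is to assess the extent of bias, and only disagreement leads to any further step.

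**A reader might infer that the check says nothing about the primary endpoint.** The documents do not support that. Exact invariance at week 6 needs arm-by-visit terms, which 5h does not list. With visits pooled, the estimate does move, though only slightly and almost equally under informative and random loss.

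**A reader might also infer that baseline-only patients are definitely excluded.** Exclusion is the likelier reading, because the dependent variable is change and two time points are required. But the dropping is qualified, the sentence on imputing patients with missing data makes no exception, and 5e allows an end-of-study MCCB that some early leavers might have. Section 5j mentions safety measures at termination without saying that nothing else is collected.

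**Expected loss is small, and 8:1 is an unlikely split.** Both are true, and they limit the size of the point.

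**Conclusion.** The point holds in this form. The planned comparison sets one MAR analysis against another, so it can hardly show bias from loss that depends on the unseen MCCB score, and the documents plan no MNAR sensitivity analysis. Read as weeks 6 and 12, the check moves the primary result by nothing (arm-by-visit terms) or by about 0.01 SD of change (visits pooled). Baseline-only patients are probably in neither analysis, although the test is called intent-to-treat.

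The size depends on balance. With nine baseline-only losses the week-6 bias is negligible at 5:4, small at 6:3 and material at 8:1. It would be wrong to infer a general inflation of type I error: only the lopsided case stands out. These figures rest on an assumed 0.96 SD deficit in lost patients and no true effect, and show scale rather than a forecast. Confidence is high that the check cannot do its stated job, and moderate on the handling of baseline-only patients and on the visit terms, where the text is open. This should be changed, but it does not invalidate the primary test.

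**What to change.** 1. Reconcile the Missing data paragraph with the MCCB schedule, so that it refers to weeks 6 and 12.
2. Keep the MAR imputation as a consistency check. Add recorded mood and side-effect variables to the imputation model, name them, and state: *Agreement between the two analyses does not exclude informative dropout.*
3. Pre-specify one MNAR sensitivity analysis of the week-6 MCCB difference that includes all randomised patients, including those with baseline MCCB only. One option is delta-adjusted imputation with separate shifts by arm over a stated grid (for example 0 to −1 SD of change in steps of 0.25) and a reported tipping point. Reference-based imputation is an acceptable alternative.

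Describing missingness by arm and reason, whatever the comparison shows, is also useful but does not test MNAR.

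The cost is statistical text and code, with no new visits or procedures. The downside is a little more analysis work and a sensitivity result that may be less favourable.

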### e) Study Endpoints

The primary endpoints related to the safety and efficacy on neurocognitive functioning of pramipexole will be measured. Neurocognitive performance on the MATRICS Consensus Cognitive Battery will be measured at baseline, week 6, and 12 (or end of study). Safety measures will be assessed at each visit throughout the study. Co-primary measures of everyday functioning (described below) will be assessed at baseline and week 12 (or end of study).

|   |   |  |
|---|---|--|
|  | Protocol Title:                           | 1/2-Pramipexole in Bipolar Disorder: Targeting Cognition (PRAM-BD) |
|   | Principal Investigator Name/Contact Info: | [name]   |
|   | Primary Contact Name/Contact Info:        | [name]
[contact]                          |
|   | Date Revised:                             | March 23, 2016 – date of IRB approval May 6, 2017                  |
|   | Study Number:                             | GCO 13-0237, HS 14-00328   |

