## f) Procedures Involved in the Human Research

All eligible participants will undergo study visits at screening, baseline (week 0), week 1, week 2, week 3, week 4, week 6, week 8, and week 12, (end of study).

Randomization will be conducted via a computer generated program and all study staff will be blinded unless un-blinding is required for safety reasons. Subjects will be randomized on a 1:1 ratio with stratification for concomitant antipsychotic status and depression at baseline (HRSD <8 vs  $\geq$  8). Study drug will be blinded and matched to placebo. Adapting from our previous work in BD and according to package labeling, the dosage titration schedule will be slow and flexible. Dosing will be initiated at 0.25 mg QHS on night one, followed by 0.25 mg BID day two onward, and increased every week to a target of 4.5 mg/day. As compared with our previous maximum 1.5 mg/day ([name] et al. 2012), we opted to allow up to 4.5 mg/day (the maximum approved dosage in Parkinson’s disease) to ensure adequate target engagement. We are familiar with this dose range, as 4.5 mg/day was allowed in our study in BD depression (Goldberg et al. 2004). Dosing will be flexible based on side effects; however, if 1.5 mg/day cannot be tolerated, the subject will be discontinued. Titration will occur up to week 6 and then efforts will be made to maintain the same dose until the completion of the trial (week 12).

Measures are described in detail below:

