### Clinical/Symptom Measures

- Structured Clinical Interview for the DSM-IV (SCID-IV) – (*screening*)
- Symptom rating scales: Young Mania Rating Scale (YMRS); Hamilton Rating Scale for Depression (HRSD); Brief Psychiatric Rating Scale (BPRS) – (*all visits*)
- Smoking questionnaire – (*screening, baseline, week 6, week 12*)

|   |   |  |
|---|---|--|
|  | Protocol Title:                           | 1/2-Pramipexole in Bipolar Disorder: Targeting Cognition (PRAM-BD) |
|   | Principal Investigator Name/Contact Info: | [name]   |
|   | Primary Contact Name/Contact Info:        | [name]
[contact]                          |
|   | Date Revised:                             | March 23, 2016 – date of IRB approval May 6, 2017                  |
|   | Study Number:                             | GCO 13-0237, HS 14-00328   |

Neurocognitive/Functional Measures

- Screening cognitive battery (see inclusion criteria 4.) – (*screening*)
- Cognitive assessment: MATRICS Consensus Cognitive Battery (MCCB- plus; see description below) – (*baseline, week 6, week 12*)
- The Probabilistic Stimulus Selection Task – (*baseline, week 6, week 12*)
- UCSD Performance Skills Assessment (UPSA) – (*baseline, week 12*)
- The World Health Organization Disability Assessment Schedule (WHODAS 2.0) – (*baseline, week 12*)

| The MATRICS Consensus Cognitive Battery | Domain               | Note/Description               |
|---|-----------------------------|---------------------------------------|
| Category Fluency                                      | Speed of Processing         | Total animals in 60 seconds           |
| BACS Symbol Coding                                    | Speed of Processing         | Matching numbers to symbols           |
| Trail Making Test Part A                              | Speed of Processing         | Dot-to-dot: Numbers only              |
| CPT-Identical Pairs                                   | Attention/Vigilance         | Computerized numeric stimuli          |
| Letter-Number Span                                    | Working Memory              | Recoding numbers and letters in order |
| WMS-III Spatial Span                                  | Working Memory              | Visual sequence forward and backward  |
| Hopkins Verbal Learning (HVLT)                        | Verbal Learning             | 12 word list x 3                      |

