|   | Study Number:                             | GCO 13-0237, HS 14-00328   |

patients on pramipexole vs. patients on placebo. This will be tested in an intent-to-treat analysis using a 0.05 level two-tailed test based on a mixed effects regression model, with patients considered to be a random effect, and randomization group a fixed effect. In order to preserve statistical power, change in MCCB Composite will be used as the dependent variable; however, secondary analyses will be conducted for MCCB domain scores and measure of reward processing. The use of two post baseline evaluations (weeks 6 and 12) and the ability of the model to incorporate all available data, also improves efficiency (i.e., power). This approach will also be employed in subsequent comparisons of specific domains and for measures of reward processing. These additional analyses will be conducted at a nominal 0.05 level and will focus on enhancing interpretation of the primary analysis by highlighting the specific domains most affected by pramipexole. Since randomization is stratified by concomitant antipsychotic use and baseline depression status, indicators of stratification will be included in the model as fixed effects.

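### The missing-data check imputes a week 8 MCCB score from a week 4 score, but neither is scheduled, and moving the labels to weeks 6 and 12 still leaves the primary week 6 score unimputed

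*Combined protocol and SAP*

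**What the plan says.** Section 5(e), Study Endpoints, fixes the assessment times: "Neurocognitive performance on the MATRICS Consensus Cognitive Battery will be measured at baseline, week 6, and 12 (or end of study". In section 5(f), the measures-list entry "Cognitive assessment: MATRICS Consensus Cognitive Battery (MCCB- plus; see description below" carries the same three times. The visit schedule in 5(f) does include weeks 4 and 8 ("week 1, week 2, week 3, week 4, week 6, week 8, and week 12, (end of study"), but no MCCB is listed at either.

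Under Primary hypothesis testing in section 5(h), the efficacy outcome is defined by "The primary outcome for efficacy is change in cognition from baseline to week 6 (MCCB Composite". The analysis is described by "This will be tested in an intent-to-treat analysis using a 0.05 level two-tailed test" from a mixed effects model, and the text cites "The use of two post baseline evaluations (weeks 6 and 12) and the ability of the model to incorporate all available data" as a gain in efficiency.

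The Missing data paragraph of 5(h) uses different weeks. It discusses patients who have a week 4 evaluation but lack week 8, and says "we will impute missing week 8 values". The method is given by "Patients with missing data will have their 8 week MCCB score imputed via multiple imputation assuming that the data are MAR". Imputation is done separately in each arm. The exact model is to be settled before outcome data are seen, but its predictors must include the baseline and week 4 MCCB scores. A closing paragraph says that missing data can be incorporated only for patients with at least two time points, and that patients with baseline data alone may be left out of analyses.

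**The concern.** This imputation is the only missing-data sensitivity analysis in the plan. Its stated purpose is to show how far missing data have biased the result, by comparing the analysis with and without imputation. Its target and one of its two named predictors do not exist in the assessment schedule.

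The natural reaction is to read 4 and 8 as 6 and 12. That yields a runnable analysis aimed at the later visit, while the primary outcome is at week 6. If the two analyses then agreed, the agreement could be taken as reassurance about the primary result, although no missing primary score had been imputed.

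**Working it through.** **1. Compare the weeks.**

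| Item | Source | Weeks |
|---|---|---|
| MCCB schedule | 5(e); measures list in 5(f) | 0, 6, 12 |
| Primary outcome | 5(h), Primary hypothesis testing | 6 |
| Post-baseline data in the mixed model | 5(h), Primary hypothesis testing | 6, 12 |
| Imputation target | 5(h), Missing data | 8 |
| Required predictors | 5(h), Missing data | 0, 4 |
| Expected attrition, fewer than 10 | 5(h), Missing data | 8 |

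Of the imputation weeks {0, 4, 8}, only baseline is in {0, 6, 12}. The rule cannot be executed.

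**2. Try the available readings.**

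- 4 and 8 read as 6 and 12: the target is week 12, predicted from baseline and week 6. A patient missing only week 6 has nothing imputed. A patient missing both visits lacks a required predictor. Week 6 is never a target.
- 8 read as 6, with 4 kept: the target is right, but the week 4 predictor does not exist.
- An early end-of-study MCCB might fall near week 4 or 8 for a patient who stops early, but patients in general would have no such score.

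**3. What the relabelled check could move.** When week 6 is missing, nothing is imputed and the change is zero by definition. That leaves patients with week 6 observed and week 12 missing.

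*Model with visit and group-by-visit terms* (not listed in the plan): completing week 12 leaves the week 6 contrast essentially unchanged. In 600 simulated trials the change was 0.000 SD.

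*Group-plus-strata model, as listed:* one pooled group effect averages both visits, so completing week 12 changes the weighting. Assume 50 per arm and all correlations between scores equal to 0.8. The two change scores then have correlation (0.8 − 0.8 − 0.8 + 1)/(2 − 1.6) = 0.2/0.4 = 0.5. A patient with both visits contributes weight 1/(1 + 0.5) = 0.667 to each visit; a patient with one visit contributes weight 1. Assume 7 missing week 12 on pramipexole and 2 on placebo, unrelated to score (9 in all, taking the week 8 forecast over to week 12). The stratum terms are ignored.

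- Pramipexole: week 6 weight 43 × 0.667 + 7 = 35.67; week 12 weight 28.67; week 12 share 28.67/64.33 = 0.446.
- Placebo: week 6 weight 48 × 0.667 + 2 = 34; week 12 weight 32; week 12 share 32/66 = 0.485.
- After imputation both shares are 0.500, so they rise by 0.0544 and 0.0152.

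Mean shift = (week 6 to 12 gain on pramipexole) × 0.0544 − (gain on placebo) × 0.0152, in SD of change:

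- no gain in either arm: 0;
- assumed practice gain of 0.3 in both arms: 0.3 × (0.0544 − 0.0152) = 0.012;
- the same practice gain plus an assumed drug effect growing from 0.3 to 0.8, so a gain of 0.8 on pramipexole: 0.8 × 0.0544 − 0.3 × 0.0152 = 0.039.

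Simulation gives about 0.012 and 0.04 in these last two cases. For scale, the full-data standard error of the contrast is √(2/50) = 0.20. These shifts come from reweighting the visits. They carry no information on whether patients with missing week 6 scores differ from the rest.

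**4. The plan's power figure.** Φ(0.55 × √(50/2) − 1.96) = Φ(0.79) = 78.5%, in line with the stated approximate 80%. It does not depend on the imputation rule.

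**The case against.** The strongest reply is that this is a labelling slip in a secondary check. The primary mixed model names weeks 6 and 12 and stays runnable. The closing Missing data paragraph allows any patient with two time points to contribute, which covers baseline plus week 12 with week 6 missing. The plan also leaves the imputation model to be settled before outcome data are seen, so there is a natural moment to correct it.

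Most of this stands, and it limits the point. A reader might infer that the primary analysis is broken, or that a missing week 6 score is not handled at all. Neither follows: lacking an imputation rule is different from lacking any handling. What the reply does not rescue is the check itself. The week 4 predictor is a fixed requirement rather than a deferred detail, and relabelling does not make week 6 a target.

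A reader might also infer that the relabelled check could never change the tested effect. That holds only with group-by-visit terms; under the model as listed, the pooled effect can move a little, as shown above.

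Nor does leaving out baseline-only patients by itself break the intent-to-treat analysis. In a change-score model such a patient has no outcome, and imputing from baseline alone did not reduce bias in an illustrative simulation (0.09 SD with the mixed model, 0.09 SD with that imputation). It calls for a clarifying sentence.

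Finally, assuming MAR openly is a legitimate choice. Agreement between two MAR analyses is weak evidence against dropout that depends on the unseen score, but a non-MAR analysis would be an addition to the plan and not the correction of an error.

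**Conclusion.** Wrong as written, and it should be fixed before the analysis. The only planned missing-data sensitivity analysis names two post-baseline MCCB weeks, 4 and 8, and neither is in the schedule. Changing the labels to 6 and 12 leaves a missing primary score without an imputation rule. Both findings come from comparing sections of the plan and rest on no modelling.

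The shifts of 0.012 and 0.039 SD are illustrations under assumed correlations, gains and a 7 versus 2 split. They show only that the relabelled check is not strictly inert under the listed model. A reader might infer from them, or from the attrition forecast, that the trial's result would be biased by some amount or in some direction. The documents do not support this: they give no split by arm, no reasons for dropout and no forecast for week 6 or week 12.

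**What to change.** **Required, in the Missing data paragraph of 5(h):**

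- Replace weeks 4 and 8 by the scheduled MCCB weeks 6 and 12 throughout.
- Impute missing week 6 (primary) and week 12 composites, separately by arm, from the baseline MCCB and from the other post-baseline MCCB when it is observed.
- Restate expected attrition for weeks 6 and 12.

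**To clarify:**

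- Whether baseline-only patients enter this sensitivity analysis, given the intent-to-treat label.
- Whether an MCCB given early as an end-of-study assessment counts as week 6, week 12 or neither.

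**Optional, not corrections:**

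- When the imputation model is fixed, consider the stratification factors and the HRSD and YMRS ratings collected before dropout as extra predictors. Section 5(j) ties discontinuation to those ratings. Keep the list short, given 50 patients per arm.
- Consider one pre-specified non-MAR analysis, for example a delta-adjusted one.

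The cost is SAP wording and a few hours of programming, with no new data or visits.
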